	No Response	Response
No Toxicity	77	16
Toxicity	26	5

A flat Dirichlet prior distribution for experimental Panitumumab was chosen reflective of information from the equivalent of 4 patients with the same marginal distributions as for Panitumumab (e.g., RR rate of 17% and toxicity rate of 25%).

This regimen of Panitumumab will be considered worthy of further investigation if it elicits an increase in RR to 25% with acceptable toxicity. A 25% toxicity rate is considered unacceptable. Thus, interim monitoring rules, assuming the prior distributions above, were constructed that meet the following two conditions,

- 1) $\Pr(\emptyset_S, \text{Toxicity} < \emptyset_E, \text{Toxicity} \mid \text{data}) > 0.95$ and,
- 2) $\Pr(\emptyset_S, \text{Response} < \emptyset_E, \text{Response} \mid \text{data}) < 0.05$

Where $\emptyset_{E, \text{Toxicity}}$ and $\emptyset_{E, \text{Response}}$ are the true toxicity and response rates for Panitumumab, respectively. The first rule provides for stopping the study if excessive toxicity is highly probable (i.e., probability $> 95\%$) for Panitumumab. The second condition will stop the study early if the data suggest that it is unlikely (i.e., probability $< 5\%$) that response rate

of the drug is 17%. Assuming the minimum number of patients is 1, the maximum number of patients is 17 and the cohort size is 1.

The monitoring rule for the toxicity rate, based on these assumptions and monitoring conditions above is found in the following table. For example, accrual will cease if 4 or more patients experience toxicities among the first 5 patients treated or if 6 or more patients experience toxicities among the first 10 patients.

Stop accrual if the number of toxicities is equal to or greater than indicated (i.e., # toxicities) among the number of patients evaluated (i.e., # patients)						
# Toxicities	3-4	4-6	5-9	6-11	17-14	8-16
# Patients	3-4	5-6	7-9	10-11	12-14	15-16

Monitoring the response rate, based on the above assumptions and monitoring will begin after 1 patient is treated (on an intent-to-treat basis). Following this rule, the trial will be terminated if $[\# \text{ Response}] / [\# \text{ patients evaluated}] \leq 0/8$. For example, accrual will cease if 0 or fewer patients experience a response in the first 8 patients treated.

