Multc Lean Desktop (version 2.0.0) was used to generate the toxicity and futility stopping boundaries and the OC table. In order to utilize the software for the design, a beta (21, 103) prior was assumed for the historical control response rate and a beta (31, 93) prior was assumed for the historical control toxicity rate.

The probability of stopping the study early if the true response rate of the Panitumumab was not better than 17% was 35%. Probabilities of stopping early for high true toxicity rates (i.e., 37%) were 57% when the true RR rate was 17% and 48% when true RR was 25%.

Operating characteristics for simultaneous monitoring response and toxicity rates for patients treated with Panitumumab.				
True RR	True Toxicity Rate	True Probability Vector (RR/TX, RR/NTX, NRR/TX, NRR/NTX)	Probability of Stopping	Average number of patients treated
8%	12%	(0.010,0.070,0.110,0.810)	0.5174	12
8%	25%	(0.020,0.060,0.230,0.690)	0.5637	12
8%	37%	(0.030,0.050,0.340,0.580)	0.6885	10
17%	12%	(0.020,0.150,0.099,0.730)	0.2319	15
17%	25%	(0.042,0.127,0.207,0.622)	0.3055	14
17%	37%	(0.062,0.107,0.307,0.523)	0.5042	12
25%	12%	(0.030,0.220,0.090,0.660)	0.1078	16
25%	25%	(0.062,0.187,0.187,0.562)	0.1934	15
25%	37%	(0.092,0.157,0.277,0.472)	0.4241	13

Where Will Participants Be Enrolled:

Only at MDACC

Is this an NCI-Cancer Therapy Evaluation Protocol (CTEP)? No

Is this an NCI-Division of Cancer Prevention Protocol (DCP)? No

Estimated Accrual:

Total Accrual at MDACC: 27

Estimated monthly accrual at MDACC: 1-2

Accrual Comments:

The total accrual for this study is 27. There are 10 patients already enrolled and 3 have been treated with combination therapy, and 17 patients are to be enrolled for the single agent treatment.

Do you expect your target population to include non-english speaking participants? No

Location of Treatment:

This protocol is performed on an Outpatient basis.

Length of Stay: What is the length & frequency of hospitalization?

NA

Return Visits: How often must participants come to MDACC?

Every 2 weeks

Home Care: Specify what, if any, treatment may be given at home.

NA

Name of Person at MDACC Responsible for Data Management: [[name]](#)

Prior protocol at M. D. Anderson:

Has the Principal Investigator ever had a clinical or behavioral protocol at MDACC that accrued patients?
Yes

Data Monitoring Committee:

Is treatment assignment randomized? No

Is this a blinded or double-blinded study? No

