Does this protocol have a schedule for interim and final analysis? Yes

Please describe:

Amended Study Design, Sample Size, Efficacy and Toxicity Monitoring as of October 1, 2012:

Response and toxicity will be monitored simultaneously using the Bayesian approach of Thall, Simon, Estey (1995, 1996) and the extension by Thall and Sung (1998). Bayesian interim futility and toxicity rules will be used. Complete details are included in the Statistical Considerations section. Data from a previous study of single agent Panitumumab in Kras wildtype colorectal cancer demonstrated a response rate for Panitumumab is approximately 17%. The toxicity rate of Panitumumab will estimate it will be approximately 25%. For the prior distribution of standard Panitumumab, we assumed a simple Dirichlet distribution and independence between OR and toxicity in 124 patients. The parameters for this prior distribution are as follows:

Dirichlet parameters for the joint prior distribution of objective response and toxicity rate assuming information on 124 patients and independence among response and toxicity for Panitumumab.

	No Response	Response
No Toxicity	77	16
Toxicity	26	5

A flat Dirichlet prior distribution for experimental Panitumumab was chosen reflective of information from the equivalent of 4 patients with the same marginal distributions as for Panitumumab (e.g., RR rate of 17% and toxicity rate of 25%).

This regimen of Panitumumab will be considered worthy of further investigation if it elicits an increase in RR to 25% with acceptable toxicity. A 25% toxicity rate is considered unacceptable. Thus, interim monitoring rules, assuming the prior distributions above, were constructed that meet the following two conditions,

- 1) $\Pr(\emptyset S, \text{Toxicity} < \emptyset E, \text{Toxicity} \mid \text{data}) > 0.95$ and,
- 2) $\Pr(\emptyset S, \text{Response} < \emptyset E, \text{Response} \mid \text{data}) < 0.05$

Where $\emptyset E, \text{Toxicity}$ and $\emptyset E, \text{Response}$ are the true toxicity and response rates for Panitumumab, respectively. The first rule provides for stopping the study if excessive toxicity is highly probable (i.e., probability >95%) for Panitumumab. The second condition will stop the study early if the data suggest that it is unlikely (i.e., probability < 5%) that response rate of the drug is 17%. Assuming the minimum number of patients is 1, the maximum number of patients is 17 and the cohort size is 1.

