The monitoring rule for the toxicity rate, based on these assumptions and monitoring conditions above is found in the following table. For example, accrual will cease if 4 or more patients experience toxicities among the first 5 patients treated or if 6 or more patients experience toxicities among the first 10 patients.

Stop accrual if the number of toxicities is equal to or greater than indicated (i.e., # toxicities) among the number of patients evaluated (i.e., # patients)

# Toxicities	3-4	4-6	5-9	6-11	17-14	8-16
# Patients	3-4	5-6	7-9	10-11	12-14	15-16

Monitoring the response rate, based on the above assumptions and monitoring will begin after 1 patient is treated (on an intent-to-treat basis). Following this rule, the trial will be terminated if $[\# \text{Response}]/[\# \text{patients evaluated}] \leq 0/8$. For example, accrual will cease if 0 or fewer patients experience a response in the first 8 patients treated.

Radiation Safety:

Does this study involve the administration of radioisotopes or a radioisotope labeled agent?	No
----------------------------------------------------------------------------------------------	----

Is the radioactive compound (or drug) FDA approved and/or commercially available?

No

Investigational New Drugs:

Does this protocol require an IND? Yes

Please list the IND holder and provide the IND number:

IND Holder: MDACC

IND Number: 109220

Investigational Device:

Is the Investigational Device approved by the FDA? N/A

Is the Investigational Device being used in the manner approved by the FDA? N/A

Has the Investigational Device been modified in a manner not approved by the FDA? N/A

Name of Device: NA

Manufacturer: NA

What is the FDA Status of the Investigational Device? Not Marketed.

Is the study being conducted under an Investigational Device Exemption (IDE)? No

IDE Holder: NA

IDE Number: NA

Risk Assessment:

Please answer the following questions regarding the Investigational Device.

Intended as an implant? No

Purported or represented to be for use supporting or sustaining human life? No

For use of substantial importance in diagnosing, curing, mitigating, or treating disease, or otherwise preventing impairment of human health? No

You may attach sponsor documentation of the risk assessment:

NA

Will participant be charged for the Investigational Device? No

Sponsorship and Support Information:

Does the Study have a Sponsor or Supporter? Yes

Sponsor or Supporter: Amgen
Type(s) of Support: Funds
Agent

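### The futility bound of 0/8 and four of the toxicity bounds do not follow from the stated 4-patient prior and the 0.05/0.95 cut-offs

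*Combined protocol and SAP*

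**What the plan says.** All the inputs are in the combined protocol and SAP, Statistical Considerations, Sample Size and Endpoint Monitoring. Most of this text is repeated under the interim and final analysis question of the Data Monitoring Committee section.

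- **Trial-arm prior:** "A flat Dirichlet prior distribution for experimental Panitumumab was chosen reflective of information from the equivalent of 4 patients". Its marginal means are those of the historical data (17% response, 25% toxicity).
- **Control prior for response, as used in the software:** "a beta (21, 103) prior was assumed for the historical control response rate".
- **Its counterpart for toxicity, from the same sentence of the plan:** "a beta (31, 93) prior was assumed for the historical control toxicity rate".
- **Link from priors to bounds:** "Thus, interim monitoring rules, assuming the prior distributions above, were constructed that meet the following two conditions". The conditions are to stop for toxicity if the probability that trial-arm toxicity exceeds control is above 0.95, and to stop for futility if the probability that trial-arm response exceeds control is below 0.05. The toxicity table is tied to the same inputs: "The monitoring rule for the toxicity rate, based on these assumptions and monitoring conditions above is found in the following table".
- **Futility bound:** "accrual will cease if 0 or fewer patients experience a response in the first 8 patients treated".
- **Toxicity bounds:** 3 at n = 3–4, 4 at n = 5–6, 5 at n = 7–9, 6 at n = 10–11, 7 at n = 12–14 and 8 at n = 15–16.
- **Software:** one program "was used to generate the toxicity and futility stopping boundaries and the OC table".

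No other trial-arm prior is given anywhere.

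**The concern.** The stopping rule is described in two ways: as priors with cut-offs, and as explicit counts. The counts are said to be derived from the priors, so the two should agree. They lead to opposite decisions at 0/8, 0/9 and 0/10 responses and at 3/4, 4/6, 5/9 and 7/14 toxicities.

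With a look after every patient and at most 17 patients, moving the futility bound by three patients changes the operating characteristics materially. Anyone who verifies, re-runs or reports the design from its text obtains a different rule from the printed one. The trial-arm prior is also the only one of the three priors not given as beta parameters, so the discrepancy cannot be seen without recomputing the bounds.

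**Working it through.** **Inputs.** A prior worth 4 patients with means 0.17 and 0.25 has these marginals:

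- response: beta(4 × 0.17, 4 × 0.83) = beta(0.68, 3.32)
- toxicity: beta(4 × 0.25, 4 × 0.75) = beta(1, 3)

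The controls are beta(21, 103) and beta(31, 93). After x events in n patients the trial-arm posterior is beta(a + x, b + n − x). The quantity monitored is Pr(E > S), the integral over s of f_S(s) × Pr(E > s), computed numerically with E and S independent.

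**Step 1: the plan's own table.** The printed bounds were enumerated exactly, with a look after each of patients 1–16 and independent response and toxicity. All nine stopping probabilities in the operating-characteristics table come out to four decimals (printed-bounds column in step 5). This confirms how the toxicity table is read, including 7 at n = 12–14, where the cell appears as 17-14 in the text available to us. The bounds and the table therefore agree with each other.

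**Step 2: futility under the stated prior.** The rule requires a value below 0.05.

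| Responses/patients | 4-patient prior | 2-patient prior |
|---|---|---|
| 0/7 | 0.0912 | 0.0511 |
| 0/8 | 0.0754 | 0.0410 |
| 0/9 | 0.0626 | 0.0330 |
| 0/10 | 0.0520 | 0.0267 |
| 0/11 | 0.0434 | 0.0218 |

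The stated prior first stops at 0/11. The 2-patient prior first stops at 0/8, as printed.

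**Step 3: toxicity under the stated prior.** The rule requires a value above 0.95.

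| Printed bound | 4-patient prior | 2-patient prior |
|---|---|---|
| 3/4 | 0.9240 | 0.9528 |
| 4/6 | 0.9449 | 0.9639 |
| 5/9 | 0.9371 | 0.9527 |
| 7/14 | 0.9492 | 0.9594 |

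The other ten bounds for n = 3–16 agree with the stated prior. At these four sample sizes it would require 4, 5, 6 and 8 toxicities.

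**Step 4: other explanations.**

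- *Misprinted toxicity cut-off.* With beta(1, 3), stopping at 3/4 needs a cut-off below 0.9240. Not stopping at 6/12 needs one of at least 0.9326. No value satisfies both.
- *Flat taken literally.* Dirichlet(1,1,1,1) has beta(2, 2) marginals. It never stops for futility (0/17 gives 0.144), and ten of the 14 toxicity bounds change.
- *Fixed reference rates in place of the control betas.* With a 4-patient prior and fixed rates of 17% and 25%, futility first stops at 0/10, and 3/4 and 5/9 still fail.
- *Smaller weight.* Scanning in steps of 0.01 with the means held at 17% and 25%, every weight from 1.95 to 2.18 patients reproduces 0/8 and all 14 toxicity bounds. A weight of 2 gives beta(0.34, 1.66) and beta(0.5, 1.5).

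**Step 5: size.** Probability of stopping early:

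| True RR / toxicity | Printed bounds | Bounds from the 4-patient prior |
|---|---|---|
| 8% / 12% | 0.5174 | 0.4017 |
| 8% / 25% | 0.5637 | 0.4401 |
| 8% / 37% | 0.6885 | 0.5776 |
| 17% / 12% | 0.2319 | 0.1318 |
| 17% / 25% | 0.3055 | 0.1876 |
| 17% / 37% | 0.5042 | 0.3871 |
| 25% / 12% | 0.1078 | 0.0455 |
| 25% / 25% | 0.1934 | 0.1068 |
| 25% / 37% | 0.4241 | 0.3262 |

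- Futility alone at 17% response: 0.83^8 = 22.5% against 0.83^11 = 12.9%.
- Futility alone at 25% response: 0.75^8 = 10.0% against 0.75^11 = 4.2%.
- Toxicity rule alone at 37% true toxicity: 36.0% against 29.7%.
- Mean number treated at 17% / 25%: 14.1 against 15.7.

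**The case against.** The strongest reply is that the counts are the rule and the prior only explains where they came from. A monitor applies 0/8 and the toxicity table without needing a prior, and the properties of those counts are disclosed correctly in the operating-characteristics table. On that view the right-hand column of step 5 describes a design that was probably never run, and if the prior sentence is the error the effect on conduct is nil. The printed toxicity bounds stop sooner than the stated prior would, so they create no safety shortfall. The sample-size test against a null of 1% or less does not use this prior, and this version is already closed to new patients. Two of the four toxicity misses are narrow (0.9449 and 0.9492).

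Most of this stands and limits the weight of the point. It does not remove the error: the document says the counts meet conditions that five of them fail. The futility miss is not narrow (0.075 against 0.05), and neither are 3/4 and 5/9.

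It is also fair to say that the 2-patient weight is an inference. The scan assumes one common weight and fixed means, and a range of weights fits. In addition, the sentence above the operating-characteristics table gives 35%, 57% and 48% where the table has 0.3055, 0.5042 and 0.4241. That is a separate discrepancy, but it shows that the prior sentence is not the only text out of step with the table.

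**Conclusion.** The concern holds. With the documented priors and cut-offs, the futility bound is 0/11 rather than 0/8, and the toxicity bounds at n = 4, 6, 9 and 14 are each one event higher than printed. The printed bounds and the operating-characteristics table agree with each other, so the description of the trial-arm prior is the likely outlier; a weight of about 2 patients would explain everything printed. The documents do not show which was intended.

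The gap between the two readings in the chance of stopping early is 6 to 12 percentage points across the nine tabulated scenarios (11.8 points at 17% / 25%). This rests on reading the trial-arm prior as beta marginals of total weight 4 with means 17% and 25%, on the stated control betas, and on independent response and toxicity. It should be fixed, mainly so that the design can be reproduced and reported correctly.

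**What to change.** Check the software input for the trial-arm prior, then reconcile the passages in one of two ways.

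1. **If the printed bounds are the intended ones:** correct the prior weight in Sample Size and Endpoint Monitoring and in its repeat under Data Monitoring Committee. State the trial-arm beta parameters actually entered, next to the two control betas, and remove the word flat, which conflicts with means of 17% and 25%. This is a wording change in two places; conduct and the operating-characteristics table stay as they are.
2. **If the 4-patient prior was intended:** regenerate the futility bound, the toxicity bounds and the operating-characteristics table, and say openly that both rules then act later. The cost is a software rerun, new tables and weaker toxicity stopping (29.7% instead of 36.0% for the toxicity rule alone at 37% true toxicity).

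In either case, check the toxicity-table cell that reads 17-14 against the source. It may only be an artefact of text extraction; the pattern and the operating-characteristics table point to a threshold of 7 for n = 12–14.

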- 11 Hematology: hemoglobin, platelets, and absolute neutrophil count. Chemistry: creatinine, total bilirubin, AST, ALT, Magnesium, Potassium, Calcium. In patients with known Gilbert's syndrome direct bilirubin will also be performed
- 12 At time of or up to 10 days after decision to discontinue study treatment.
13. Up to 35 days from last dose of study medication.

Statistical Considerations:

Study design and Sample Size:

Amended Study Design, Sample Size, Efficacy and Toxicity Monitoring as of October 1, 2012:

The primary endpoint of this phase II, single arm study is response rate (RR) for patients treated with single-agent Panitumumab. Patients will be evaluated for up to 8 cycles from their first dose, and a patient will be considered as a non-responder if no PR or CR has been documented after 8 cycles of treatment. Patients who withdraw early will be included in the ITT analysis. Based on our current data with a null hypothesis of $\leq 1\%$ RR to an inactive drug for refractory patients, a sample size of 17 patients with Panitumumab would be required to demonstrate a response rate of 17% using a binomial one-sample test with a two-sided alpha of 0.05 and power of 90%.

The primary adverse event to be monitored will be the toxicity rate. Toxicities to be included in toxicity monitoring include definite or probably treatment-related grade 3 or 4 non-hematological toxicities, excluding grade 3 rash and grade 3 hypomagnesemia, which are both expected and manageable toxicities. Only toxicities during the first 4 cycles of therapy will be used in toxicity monitoring. Accrual is estimated at 1 to 2 patients per month.

Sample Size and Endpoint Monitoring

Response and toxicity will be monitored simultaneously using the Bayesian approach of Thall, Simon, Estey (1995, 1996) and the extension by Thall and Sung (1998). Data from a previous study of single agent Panitumumab in Kras wildtype colorectal cancer demonstrated a response rate for Panitumumab is approximately 17%. The toxicity rate of Panitumumab will estimate it will be approximately 25%. For the prior distribution of standard Panitumumab, we assumed a simple Dirichlet distribution and independence between OR and toxicity in 124 patients. The parameters for this prior distribution are as follows:

Dirichlet parameters for the joint prior distribution of objective response and toxicity rate assuming information on 124 patients and independence among response and toxicity for Panitumumab.

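### The stated 90% power is a normal approximation that the exact test does not reach at n = 17 (81%), and the 25% criterion has no responder count and no link to that test

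*Combined protocol and SAP*

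**What the plan says.** Statistical Considerations, under Study design and Sample Size (amended October 1, 2012), takes a null RR of at most 1% for an inactive drug in refractory patients. The number needed to show an RR of 17% is put at 17 patients, "using a binomial one-sample test with a two-sided alpha of 0.05 and power of 90"%. No rejection count is given.

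Sample Size and Endpoint Monitoring then treats about 17% as the historical rate for panitumumab: "a beta (21, 103) prior was assumed for the historical control response rate". It sets the bar for further work at a higher rate: "This regimen of Panitumumab will be considered worthy of further investigation if it elicits an increase in RR to 25% with acceptable toxicity". The Data Monitoring Committee section repeats this. Neither place says how many responders meet the bar. The only response count in the plan is the futility stop: "accrual will cease if 0 or fewer patients experience a response in the first 8 patients treated".

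The table of operating characteristics includes a true RR of 25% as a scenario. It reports only the probability of stopping and the average number treated, not the chance of meeting the 25% criterion.

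**The concern.** A reader at the end of the trial has two benchmarks and no rule joining them. The sized test asks whether RR exceeds 1%. The statement on further investigation asks for 25%, with 17% as the starting point. The plan does not say what rejecting 1% contributes to the decision, nor what observed result counts as 25%.

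The stated power is also suspect on sight. With n = 17 and a null rate of 1%, the expected number of responders under the null is 0.17. A normal approximation cannot be trusted there, and the binomial test can move only in whole responders.

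At stake is how the result is interpreted. A modest result such as 3/17 could be presented as a positive test with 90% planned power, or as falling short of the plan's own bar. Accrual closed in April 2016, so a count chosen now could be chosen with the responses already known.

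**Working it through.** **Inputs.** From Study design and Sample Size: p0 = 0.01, p1 = 0.17, n = 17, two-sided alpha 0.05 (upper tail 0.025). From Sample Size and Endpoint Monitoring: 25% criterion, stop at 0/8, maximum 17, cohort size 1. True RRs of 8%, 17% and 25% are those of the operating-characteristics table.

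**1. Reproduce the 90%.** One-sample normal approximation, no continuity correction:

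power = Φ{[(p1 − p0)√n − 1.96√(p0(1 − p0))] / √(p1(1 − p1))} = Φ{[0.16 × 4.123 − 1.96 × 0.0995] / 0.3756} = Φ(1.237) = 0.892.

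The same formula gives n = 17.9 for 90%. So the figure has a traceable source. Its critical count is 17 × 0.01 + 1.96√(17 × 0.01 × 0.99) = 0.97, which means rejecting at 1/17.

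**2. Exact test.**

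- Reject at ≥1/17: size = 1 − 0.99^17 = 0.157, which breaks alpha.
- Reject at ≥2/17: size = 1 − 0.99^17 − 17(0.01)(0.99^16) = 0.0123. Power at 17% = 1 − 0.83^17 − 17(0.17)(0.83^16) = 0.811.

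The cut-off is 2/17 whether the upper tail is 0.025 or 0.05. No count at n = 17 gives both the stated alpha and 90% power. The smallest n with exact power of at least 90% is 22 (≥2 responders, size 0.0202, power 0.909).

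**3. Add the 0/8 stop, taken as binding.** P(not stopped and X ≥ r) = P(X17 ≥ r) − (1 − p)^8 × P(X9 ≥ r). For r = 2, p = 0.17: 0.8113 − 0.2252 × 0.4685 = 0.706.

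**4. The 25% criterion.** 0.25 × 17 = 4.25, so the count could be 4/17 (23.5%) or 5/17 (29.4%). The sized test already rejects at 2/17 (11.8%). After the 0/8 stop:

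| | True RR 8% | 17% | 25% |
|---|---|---|---|
| Reject 1% (≥2/17) | 32% | 71% | 88% |
| Meet ≥4/17 | 4.0% | 31% | 63% |
| Meet ≥5/17 | 0.9% | 15% | 42% |
| Reject 1% but miss ≥4/17 (2–3/17) | 28% | 39% | 25% |
| Reject 1% but miss ≥5/17 (2–4/17) | 31% | 56% | 46% |

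**5. Add the toxicity stops.** This is an exact recursion over responses and toxicities, taken as independent. Limits are 3 toxicities at 3–4 patients, 4 at 5–6, 5 at 7–9, 6 at 10–11, 7 at 12–14 and 8 at 15–16; the printed entry 17-14 is read as 7. The recursion returns all nine stopping probabilities in the plan's table to four decimals. Power of the ≥2/17 rule at 17% becomes 63% at 25% toxicity (70% at 12%, 45% at 37%). The chance of 2–4/17 at 25% toxicity becomes 28%, 50% and 41% at true RR 8%, 17% and 25%.

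The prose above that table gives stopping probabilities of 35%, 57% and 48%. The closest rows of the table show 0.3055, 0.5042 and 0.4241. The recursion matches the table, not the prose.

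**6. Could n = 17 test 25% against 17%?** P(X ≥ 6 | 0.17) = 0.055, just above a one-sided 5%. P(X ≥ 7 | 0.17) = 0.016, with power P(X ≥ 7 | 0.25) = 0.107. It could not.

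**The case against.** **The power figure is not a slip.** The plan says binomial test, not exact test, and 90% agrees with a standard approximation (89.2% two-sided, 90.7% one-sided). That stands, and a reader who infers an arithmetic error goes too far. But the approximation gets there by rejecting at one responder, which does not hold the plan's alpha.

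**The 25% sentence may only motivate the monitoring design.** One sentence later the text turns to the interim rules, and 25% reappears as a scenario in the table. This reading is available. It does not close the gap: the plan nowhere says that completing accrual amounts to success, so no final rule exists under either reading.

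**The spread depends on the count chosen.** This is correct. With 4/17, the in-between outcome is not a majority at any of the three true rates. With 5/17 it is a majority only at 17%. Both are therefore shown.

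**Stronger readings that the documents do not support.** A reader might infer cut-offs as high as 7/17 (a one-sided 5% test against 17%) or 9/17 (exact lower 95% limit above 25%). The plan proposes neither, and the second would succeed about 1% of the time at a true 25%. A reader might also infer that using 17% as both target and historical rate is itself an error. Different references for monitoring and for the sized test are permissible; what is missing is a statement connecting them. Finally, the primary objective is to determine RR, and that remains answerable.

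**Conclusion.** The point holds in two parts and should be fixed.

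- The 90% power is an approximation that the exact test does not attain. At n = 17 the smallest rule that holds alpha is ≥2/17, with power 81% at a true RR of 17%, 71% after the 0/8 stop, and 63% with both stops at 25% toxicity.
- The 25% criterion cannot be applied as written. Choosing 4/17 or 5/17 moves the chance of meeting it at a true 25% from 63% to 42%, and at a true 17% from 31% to 15%. Depending on the true rate and the count, the trial has a 25% to 56% chance of rejecting 1% while missing that criterion.

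These figures assume that the 0/8 stop is binding, that each response is known before the next patient enters, and that 25% means an observed rate. The both-stops figures also assume independence of response and toxicity and the toxicity limits as read above. The consequence is confined to interpretation and reporting; estimation of RR is unaffected.

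**What to change.** No patients need to be added.

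1. Keep the two-sided alpha of 0.05. State the rejection rule as ≥2/17 with attained one-sided size 0.012. Restate the power at 17% as 81% exact (71% after the 0/8 stop), noting that 90% came from a normal approximation.
2. State that rejecting 1% shows activity only. Give the 25% criterion one responder count with exact operating characteristics. An example is ≥5/17, the smallest count with an observed rate of at least 25%, which after the 0/8 stop is met with probability 42%, 15% and 0.9% at true RR 25%, 17% and 8%. Put the same wording in the Data Monitoring Committee section.
3. Disclose that 17 patients cannot test 25% against 17%. Report RR with its exact 95% interval (for example 2/17: 1.5% to 36.4%; 5/17: 10.3% to 56.0%). Date the count relative to any review of response data and label it post hoc if it came later.
4. Reconcile the stopping probabilities in the prose with those in the table.

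The cost is wording and disclosure: the stated power becomes less favourable, and a count written after response review carries the post hoc label.

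### The sentence on early stopping at 37% toxicity gives 57% and 48%; the printed rules give 50.4% and 42.4% for any stop, and 36.0% for the toxicity rule alone

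*Combined protocol and SAP*

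**What the plan says.** The trial runs two stopping rules together. On enrolment and looks, Sample Size and Endpoint Monitoring says: "Assuming the minimum number of patients is 1, the maximum number of patients is 17 and the cohort size is 1".

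- **Toxicity rule.** "The first rule provides for stopping the study if excessive toxicity is highly probable". The worked example is that "accrual will cease if 4 or more patients experience toxicities among the first 5 patients treated or if 6 or more patients experience toxicities", where the second count refers to 10 patients. The boundary table counts toxicities only.
- **Futility rule.** "accrual will cease if 0 or fewer patients experience a response in the first 8 patients treated".

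Performance is reported twice. The prose says "Probabilities of stopping early for high true toxicity rates (i.e., 37%) were 57% when the true RR rate was 17" per cent, and "48% when true RR was 25" per cent. The table below it is headed "Operating characteristics for simultaneous monitoring response and toxicity rates for patients treated with Panitumumab". For 37% toxicity it prints 0.5042 at a response rate of 17% and 0.4241 at 25%, in one stopping column with no breakdown by reason. No probability is given anywhere for the toxicity rule on its own.

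**The concern.** Two features of the prose sentence look wrong.

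First, its figures disagree with the table for the same two scenarios: 57% against 50.4%, and 48% against 42.4%.

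Second, it is worded as stopping because toxicity is high, yet its figures fall as the response rate rises. The toxicity rule looks only at toxicity counts. If response and toxicity are independent, its stopping probability at 37% toxicity must be the same at every response rate. The sentence therefore cannot be giving that probability.

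This is the only statement from which an investigator or oversight body could judge how often the safety rule would act on a high toxicity rate. Taken at face value it says about half the time or more.

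**Working it through.** **Inputs, all from Sample Size and Endpoint Monitoring**

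- Maximum 17 patients, assessed one at a time.
- Toxicity bounds *b*(n): 3 at n = 3–4, 4 at 5–6, 5 at 7–9, 6 at 10–11, 7 at 12–14, 8 at 15–16. The cell for 12–14 is garbled in the text available (17-14) and is read here as 7.
- Futility: stop if there are no responses in the first 8.
- True rates from the table: toxicity 12%, 25%, 37%; response 8%, 17%, 25%. The cell probabilities are close to products of the margins (for example "0.062,0.107,0.307,0.523" for 17% and 37%), so independence is used.

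**Step 1: toxicity rule alone.** Let q(n,t) be the probability of still being open after n patients with t toxicities. Then q(n,t) = q(n−1,t)(1−p) + q(n−1,t−1)p, and any mass at t ≥ *b*(n) is a stop at n. For p = 0.37:

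- n = 3: 0.37³ = 0.0507
- n = 4: 3 × 0.37³ × 0.63 = 0.0957
- n = 6: 0.0446; n = 8: 0.0277; n = 9: 0.0513; n = 11: 0.0252; n = 13: 0.0165; n = 14: 0.0318; n = 16: 0.0164

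The unrounded terms sum to 0.3600. The same recursion gives 0.0086 at 12% and 0.1036 at 25%.

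**Step 2: futility rule alone.** (1 − RR)⁸ = 0.5132, 0.2252 and 0.1001 at response rates of 8%, 17% and 25%.

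**Step 3: reproduce the plan's table.** Combined = 1 − (1 − futility)(1 − toxicity).

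| True RR | Tox 12%: computed / printed | Tox 25%: computed / printed | Tox 37%: computed / printed |
|---|---|---|---|
| 8% | 0.5174 / 0.5174 | 0.5637 / 0.5637 | 0.6885 / 0.6885 |
| 17% | 0.2319 / 0.2319 | 0.3055 / 0.3055 | 0.5042 / 0.5042 |
| 25% | 0.1078 / 0.1078 | 0.1934 / 0.1934 | 0.4241 / 0.4241 |

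All nine agree to four decimals, and all nine average sample sizes agree after rounding. The printed column is therefore the probability of a stop for either reason. Reading the garbled bound literally as 17 gives 49.1% for RR 17% and toxicity 37%, which misses the table.

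**Step 4: compare the sentence at 37% toxicity.**

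| | RR 17% | RR 25% |
|---|---|---|
| Sentence | 57% | 48% |
| Either rule (table) | 50.4% | 42.4% |
| Toxicity rule alone | 36.0% | 36.0% |
| Sentence minus table | 6.6 points | 5.6 points |
| Table minus toxicity alone | 14.4 points | 6.4 points |

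**Step 5: split by reason.** Toxicity stops at n = 8 or before total 0.2187. Giving toxicity precedence when both bounds are met at n = 8, futility stops at RR 17% are 0.2252 × (1 − 0.2187) = 17.6%, leaving 50.4% − 17.6% = 32.8% for toxicity. At RR 25%, futility is 0.1001 × (1 − 0.2187) = 7.8% and toxicity 34.6%.

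**Step 6: could the sentence come from some other toxicity rule plus the 0/8 rule?** Removing futility gives 1 − 0.43/0.7748 = 44.5% at RR 17% and 1 − 0.52/0.8999 = 42.2% at RR 25%. Allowing for rounding of the printed percentages, the ranges are 43.9–45.1% and 41.7–42.8%. They do not overlap, so under independence no single toxicity rule paired with 0/8 futility gives both figures.

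**The case against.** The strongest reply is that nothing has been mislabelled. The table's heading says that response and toxicity are monitored simultaneously, its column does not claim to show stops for toxicity, and its arithmetic is right. The prose sentence conditions on the response rate, so it can be read as describing joint scenarios in which toxicity happens to be high. The plan never states a power for the toxicity rule.

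Much of this stands. A reader might infer that the table overstates the safety rule. It does not: it reports a combined probability and says so, and what it lacks is a split by reason. A reader might also infer that 57% and 48% are simply the any-reason probabilities, with the futility rule explaining the gap between them. The documents do not support that: step 6 shows the two figures are incompatible with that account, and their source cannot be determined. Nor should the whole 12 to 21 points be attributed to futility stops, because 6 to 7 of them are the disagreement between sentence and table.

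The reply does not rescue the sentence. Read as joint scenarios, it contradicts the table; read as the toxicity rule, it is further out. Correcting it to the table's values would still leave a figure that exceeds the toxicity rule's own probability by 14 and 6 points, with nothing to tell the reader so.

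**Conclusion.** The sentence is wrong on either reading. At 37% toxicity the printed rules give 50.4% (RR 17%) and 42.4% (RR 25%) for stopping for any reason. The toxicity rule alone gives 36.0% at any response rate, so it lets a 37% toxicity rate run to full accrual, or to a futility stop, in nearly two trials in three. The table is correct.

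This rests on independence of response and toxicity, outcomes known before the next patient enters, the printed bounds taken as given, and 7 as the bound at 12 to 14 patients. Read literally as 17, that bound lowers the toxicity-only figure to about 34%, so the conclusion does not depend on it. The effect is on what the plan reports about its safety monitoring, not on how the monitoring operates.

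**What to change.** First confirm the toxicity bound at 12 to 14 patients, in Statistical Considerations and where the boundary table is repeated under Data Monitoring Committee. Then replace the sentence above the operating-characteristics table with, for example:

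> At a true toxicity rate of 37%, the probability of stopping for any reason is 50.4% at RR 17% and 42.4% at RR 25%. The toxicity rule alone stops with probability 36.0% (10.4% at 25% and 0.9% at 12% toxicity), whatever the response rate.

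Optionally, add toxicity-only and futility-only columns beside the total. Futility alone is 51.3%, 22.5% and 10.0% at response rates of 8%, 17% and 25%. If any bound is corrected, recompute all of these.

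The cost is one rerun of the operating characteristics and an edit to one sentence, plus the table if it is split. The stated safety figure becomes less favourable. The stopping rule, sample size and visits are unchanged.
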